The study protocol follows the requirements of the standard ISO 80601-2-61:2017 "Medical electrical equipment - Part 2-61: particular requirements for basic safety and essential performance of pulse oximeter equipment". As such, in this study BrOxy M and the reference device will be tested on healthy volunteers accepting to participate in a controlled desaturation study. Use of both devices will be in accordance with the limitations imposed by and instructions included in the BrOxy M and Reference device User Manual.

Due to the use of a controlled desaturation protocol foreseen by the standard ISO 80601-2-61:2017, this study is classified as an interventional post-market clinical study in accordance with Annex I of EN ISO 14155:2020.

Clinical Investigational Plan		
Protocol No.:	Version 1.0	Page 15 of 45
01M2020-CH.LMD	Date: 22 December 2020	

During the execution of the protocol, the following measurements will be acquired in continuous mode:

- 1) the SpO₂ and HR values from the reference device, and
- 2) the photoplethysmographic signals with BrOxy M.

As shown in Figure 1, the protocol provides for the maintenance of 4 plateaus at 4 different values of saturation in steps of 5% and, therefore, at 97%, 92%, 87% and 82% SpO_2 . The SpO_2 value displayed on the reference device will be used to check the saturation level reached during each plateau level. For each level, at least 30" will be expected in order to stabilize the SpO_2 value and, subsequently, the plateau will be maintained for 2.5', continuing the parallel acquisition with both the reference device and BrOxy M.

[figure not shown]

Figure 1: Time distribution of the SpO₂ measurements to be carried out on each individual subject.

Four different saturation plateaus will be used, waiting for the plateau stabilization before starting the 2.5' signal recording from which the series of 8 measurements with at least 20' of pause are extracted by means of a post-processing algorithm.

After data acquisition, up to 8 measurements for SpO₂ and HR will be selected from each plateau as follows:

- Reference device: SpO₂ and HR values will be selected starting from at least 30" after plateau stabilization, with a time interval between measurements of at least 20".
- BrOxy M: SpO₂ and HR values generated by BrOxy M will be obtained by processing the
 photoplethysmographic signals generated by the device with the BrOxy Medical software. Then,

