10 STUDY SUBJECTS

The study population will include adult healthy volunteers who will accept to participate in this oxygen desaturation study in a controlled clinical environment. At least 11 healthy subjects will be enrolled. Data collected on the first subject will not be used for accuracy measurements but will serve to finalize the test set up phase and ensure adequate recording procedures are used by site staff. On each of the remaining 10 subjects, 32 paired measurements will be performed in order to obtain a maximum of 320 "valid" measurements (see Section 17.2) which guarantees a statistically significant accuracy study (see point EE2.3.4 of the ISO 80601-2-61: 2017 standard).

To take into account invalid data and potential drop out samples up to 2 additional subjects may need to be enrolled. For this reason sample size for this study will be between a minimum of 11 and a maximum of 13 healthy volunteers.

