16 STATISTICAL ANALYSIS

16.1 OVERVIEW

Statistical analyses will be performed with SPSS, Statistical Package for the Social Sciences (SPSS Inc, Chicago, IL), by following the requirements of the standard ISO 80601-2-61:2017 ("Medical electrical equipment - Part 2-61: particular requirements for basic safety and essential performance of pulse oximeter equipment, Procedure for non-invasive laboratory testing on healthy adult volunteers).

The *significance level*, that is the probability of rejecting the null hypothesis when it is true, will be set to 0.05 (two-sided, corresponding 5% risk of concluding that a difference exists when there is no actual difference).

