16.2 ANALYSIS SETS

Analyses will regard 320 pair measurements (80 in the ambient air, and 80 for each of the four defined target levels, that will be obtained from 10 healthy subjects).

Clinical Investigational Plan			
Protocol No.:	Version 1.0	Dana 25 of 45	
01M2020-CH.LMD	Date: 22 December 2020	Page 35 of 45	

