16.3.2 Primary endpoint

The **primary endpoint** of the study regards the accuracy of SpO₂ and HR measurements of BrOxy M. The *accuracy* of the experimental BrOxy M will be evaluated by comparing SpO₂ readings of the BrOxy M to the values obtained with the secondary standard pulse oximeter equipment (Nellcor™ Bedside Respiratory Patient Monitoring System model PM1000N, Covidien LLC, USA), that is traceable to co-oximeter SaO₂ values.

The following routines will be used:

- The paired t test, to evaluate the differences between experimental and standard values: the paired sample *t*-test procedure determines whether the mean difference between two sets of observations is zero. It regards *pairs* of observations.
- Correlation analysis, to quantify the degree to which experimental and standard values are related: it is a bivariate analysis that measures the strength of the association between two variables. The degree of association is measured by a correlation coefficient (r) on a scale that varies from + 1 through 0 to 1. We expect a positive correlation: r>0.70 indicate a strong correlation, and r=1 a perfect correlation.
- Concordance correlation coefficient (CCC), to evaluate whether the experimental value is interchangeable with the standard; this statistic quantifies the agreement between a new measurement and a gold standard measurement. Also CCC varies from -1 to 1, with perfect agreement at 1.

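### For SpO2, the only figure in section 16.3.2 that reads as good performance (r above 0.70) depends on the imposed desaturation range and is compatible with 95% limits of about ±8 points

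*Combined protocol and SAP*

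**What the plan says.** The primary endpoint is the accuracy of BrOxy M for SpO2 and heart rate (HR) against the reference oximeter. Section 16.3.2 lists five analyses: paired t test, correlation, concordance correlation coefficient (CCC), Bland-Altman plot, and a regression for proportional bias.

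- **Correlation** carries a numerical reading: "We expect a positive correlation: r>0.70 indicate a strong correlation, and r=1 a perfect correlation".
- **CCC** is given a purpose, "Concordance correlation coefficient (CCC), to evaluate whether the experimental value is interchangeable with the standard", and a scale, "Also CCC varies from -1 to 1, with perfect agreement at 1", but no value that would count as adequate.
- **Bland-Altman** limits are to be drawn at 1.96 SD. Differences should be small, but small is not put into points of SpO2 or beats per minute.
- **Section 16.1** sets the significance level, which "will be set to 0.05 (two-sided, corresponding 5% risk of concluding that a difference exists". It also says the analysis follows ISO 80601-2-61:2017, and no accuracy limit from that standard is written in the plan.

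On the data, section 3 states that "the protocol provides for the maintenance of 4 plateaus at 4 different values of saturation in steps of 5" points, at 97, 92, 87 and 82%. Section 10 adds: "On each of the remaining 10 subjects, 32 paired measurements will be performed". Section 16.2 pools them: "Analyses will regard 320 pair measurements". Section 17.2 accepts a calculated SpO2 only if it lies between 80 and 100%.

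**The concern.** A correlation compares measurement error with the spread of the true values. Here the gas mixtures create that spread, so a wide range of SpO2 is guaranteed whatever the device does. A device that follows the steps only roughly can still have a high pooled r. Pearson's r also ignores a constant offset or a wrong slope. The pooled CCC does penalise offset and slope, but it too rises with the imposed range.

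The study exists to confirm performance. If the only number in the primary analysis that reads as good is one the design makes easy to reach, a report can describe SpO2 results as strong while single readings are often wrong by a full plateau step.

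**Working it through.** **Inputs.** From the plan: plateau targets 97, 92, 87 and 82% with 8 readings each (section 3, Table 1), 10 analysed subjects (section 10), 320 pairs (section 16.2), the 0.70 label (section 16.3.2) and the 80–100% filter (section 17.2). Not in the plan: the error SD of BrOxy M, which is assumed and varied.

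**The plan's own count.** 10 × 4 × 8 = 320, which agrees with section 16.2 provided ambient air is plateau I, as in Table 1. (Read literally as ambient air plus four further levels, section 16.2 would give 5 × 80 = 400.)

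**Spread of the reference.** Mean 89.5; deviations ±7.5 and ±2.5. Variance = (2 × 56.25 + 2 × 6.25)/4 = 31.25, so SD = 5.59 points.

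**r from random error, no filter.** With error independent of the reference, r = 5.59/√(31.25 + e²), where e is the error SD.

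| e (points) | r |
|---|---|
| 2 | 0.94 |
| 3 | 0.88 |
| 4 | 0.81 |
| 5 | 0.75 |
| 6 | 0.68 |
| 7 | 0.62 |

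Setting r = 0.70 gives e = 5.59 × √(1/0.49 − 1) = 5.70, or 95% limits of ±1.96 × 5.70 = ±11.2 points.

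**With the 80–100% filter.** The filter removes the largest errors near both ends of the range, so it shrinks the analysed errors and also lowers r. Simulation of 320 pairs, 80 per plateau, reference at target, invalid readings either dropped or replaced:

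| Underlying e | Handling | Mean r | Studies with r > 0.70 | Single errors above 5 points |
|---|---|---|---|---|
| 4 | no filter | 0.81 | 100% | 21% |
| 4 | dropped | 0.77 | 99.9% | 17% |
| 4 | replaced | 0.79 | 100% | 17% |
| 5 | no filter | 0.75 | 98% | 32% |
| 5 | dropped | 0.67 | 16% | 25% |
| 5 | replaced | 0.69 | 42% | 25% |
| 5.7 | dropped | 0.59 | under 1% | 30% |
| 5.7 | replaced | 0.62 | under 1% | 29% |

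With replacement, r = 0.70 at an underlying e of 4.94, which leaves an SD of 4.26 among the analysed pairs: limits of ±1.96 × 4.26 = ±8.4 points, with about a quarter of single errors above 5 points. With invalid readings dropped, the crossing is at an underlying e of about 4.7 (about 4.1 among analysed pairs, limits about ±8.0).

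**Systematic error.** Take a device that reads 89.5 + 0.1 × (reference − 89.5). Its readings run from 88.75 to 90.25, so all pass the filter. Its error is 0.9 × 7.5 = 6.75 points at 97% and 82%, and 0.9 × 2.5 = 2.25 at 92% and 87%. RMS error = 0.9 × 5.59 = 5.03. Because the reading is an exact linear function of the reference, r = 1, the value the plan calls perfect. CCC = 2 × 0.1 × 31.25/(31.25 + 0.3125) = 0.20.

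**A constant offset.** Adding 5 points to the device with e = 4 leaves r at 0.81 without the filter. With the filter, r is 0.72 (dropped) or 0.76 (replaced) for +5, and 0.70 or 0.75 for −5.

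**The case against.** The case for leaving the text alone is substantial.

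- **It is a label, not a rule.** The value is an expectation and a conventional word for strength of association, and the stated purpose of that analysis is association. This stands. A reader might infer that the study would conclude favourably whatever the accuracy, but nothing in section 16.3.2 makes 0.70 a criterion for success.
- **Other analyses would show the errors.** Bland-Altman limits, the paired t test, CCC and the proportional-bias regression are all planned. The compressing device has CCC 0.20, and a 5-point offset would be plain in the mean difference. This stands too. What is missing is a limit against which any of them is judged.
- **The filter matters.** A reader might infer from the unfiltered 5.70 that an error SD larger than a whole 5-point step would still be labelled strong. Under section 17.2 it usually would not: at an underlying SD of 5 the label is reached in 16 to 42% of studies, and at 5.7 in under 1%. The invisibility of a constant offset also weakens once the filter is applied.
- **The steps do not produce r > 0.70 unaided.** A device that does not track SpO2 has r near 0.
- **A limit may come in through the ISO standard.** The plan cites it, but quotes no figure, so this cannot be settled from the documents.

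None of this turns pooled r into evidence of accuracy.

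**Conclusion.** The point holds for SpO2 in a bounded form. HR is also part of the primary endpoint but is not stepped by design, so the argument does not extend to it.

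The 0.70 value is the only number in section 16.3.2 that reads as good performance, and it tolerates 95% limits of roughly ±8 points among the pairs actually analysed, not an error SD above one plateau step. Certain systematic errors, such as a compressed range, escape it completely.

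The figures assume 80 pairs per plateau, a reference exactly at target, and random error that is independent of the reference and equal at all levels. Other spreads move the unfiltered threshold of 5.70: to 4.71 if SpO2 were spread evenly over 82–98%, and to about 6.0 if the reference varied uniformly within the stated plateau ranges. The conclusion that r reflects the imposed range does not depend on these choices. The weakness is in how results would be read, not in the data to be collected, so it should be corrected before analysis.

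**What to change.** In section 16.3.2, and in the statistical part of the synopsis where the same analyses are listed:

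1. Remove r > 0.70 as a reading of performance. State that pooled r and CCC for SpO2 are descriptive only, because the plateaus fix the range.
2. Base the performance conclusion on the BrOxy M minus reference differences: bias, SD or RMS error, and limits of agreement. The Bland-Altman analysis already provides bias and limits. Report them pooled and by plateau for SpO2, and separately for HR.
3. Judge them against a numerical limit fixed before analysis, separately for SpO2 and HR, with its source stated. If the limit is the one in the cited ISO standard, write the figure into the plan. Without this step, removing 0.70 would leave the primary endpoint with no number at all.

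The cost is wording and one extra table by plateau. No subjects or measurements are added. The loss is a flattering statistic, and the sponsor must commit to a limit in advance.

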- Bland -Altman (B&A) plot, to evaluate the agreement between experimental and standard values; the B&A plot analysis is a simple way to evaluate a bias between the mean differences, and to estimate an agreement interval, within which 95% of the differences of the second method, compared to the first one, fall. Data can be analyzed both as unit differences plot and as percentage differences. The Bland-Altman chart is a scatterplot with the difference of the two measurements for each sample on the vertical axis and the average of the two measurements on the horizontal axis. Three horizontal reference lines are superimposed on the scatterplot one line at the average difference between the measurements, along with lines to mark the upper and lower control limits of plus and minus 1.96*the standard deviation of the measurement differences. Bland and Altman also discuss the option of using confidence interval bounds, based on the standard error of the mean, for the upper and lower reference lines. If the two methods are comparable, then differences should be small, with the mean of the differences close to 0, and show no systematic variation with the mean of the two measurements. 'Small' would be an amount that would be clinically insignificant for the factor being measured.

Clinical Investigational Plan			
Protocol No.:	Version 1.0	Page 36 of 45	
01M2020-CH.LMD	Date: 22 December 2020		

• Linear regression analysis: to give further information about any potential proportional bias about the mean differences and averages. It is a simple test for a linear trend, with the mean difference as dependent variable and the average difference as independent. The aim is to evaluate if the mean difference can be predicted from the average. The resulting coefficients indicate whether one can accept the null hypothesis that there is no proportional bias.

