At this point, once all the above conditions are verified, the values of SpO_2 and HR are calculated for the signal windows considered. These values are considered acceptable if the following conditions occur at the same time:

- Heart rate values between 40 and 280 bpm
- SpO₂ values between 80 and 100 %

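### Agreement over 80-100% SpO2 is summarised by one pooled bias and one pooled pair of limits, although four saturation levels with 80 planned pairs each would allow reporting by level

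*Combined protocol and SAP*

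**What the plan says.** Section 7.2 defines the primary comparison over a single range, 80% to 100% SpO2. Table 1 (section 3) sets four plateaus, with targets of 97%, 92%, 87% and 82% and eight paired readings each. Section 16.2 then states "Analyses will regard 320 pair measurements", 80 per level. (Read literally, its breakdown into ambient air plus four target levels would give 400. Table 1 shows that ambient air is itself one of the four, so this looks like a wording slip and does not affect the point.)

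In section 16.3.2 the paired t test "determines whether the mean difference between two sets of observations is zero". The Bland-Altman plot has three horizontal lines: the average difference, and limits 1.96 SD of the differences on either side. The interval is meant "to estimate an agreement interval, within which 95% of the differences of the second method, compared to the first one, fall". Correlation and the concordance coefficient are likewise described without any split by level.

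The same section has two partial checks. One is a regression for linear trend of the difference on the average. The other is the remark that, for comparable methods, differences should not vary systematically with the average. Nothing says what is reported if a pattern appears. Percentage differences are allowed as an option, with no rule for when to use them.

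The only stratified analysis, by skin pigmentation, is optional (16.3.3). Thirds of the SpO2 range serve only to count readings (section 3). Section 17.2 accepts only "SpO₂ values between 80 and 100" percent.

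**The concern.** Horizontal limits built from one mean and one SD describe every saturation level only if the bias and the SD of the differences are the same at all levels. The plan does not state that assumption, and its one formal check does not test it. A straight-line regression does not assess spread, and it can miss a bias that is not linear. The scatterplot can show fanning or curvature, but only by eye, and the limits stay as they are.

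The introduction (section 2) justifies this kind of monitoring by early detection of deterioration, need for long-term oxygen, and sleep apnoea, so performance at low saturation matters. If agreement is worse there, a pooled interval can look satisfactory overall while describing the lowest plateau poorly. Biases of opposite sign at different levels can also cancel in the pooled mean and in the paired t test.

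**Working it through.** **Inputs from the documents.** Ten analysed subjects (section 10: "On each of the remaining 10 subjects, 32 paired measurements will be performed"), four plateaus, eight readings per plateau; targets 97/92/87/82; limits at 1.96 SD; acceptance window 80-100%. No SD, bias or numeric margin is given, so SDs and biases below are assumptions, shown as a range.

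**The plan's own figure.** 10 × 4 × 8 = 320 pairs, and 10 × 8 = 80 per plateau. It reproduces.

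**Formulas, equal weight per plateau.** With bias b_k and SD s_k at plateau k:
- pooled mean M = mean(b_k)
- pooled SD S = √[mean(s_k²) + mean((b_k − M)²)]
- limits M ± 1.96 S
- coverage at k = Φ((upper − b_k)/s_k) − Φ((lower − b_k)/s_k)

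For the window, the reference is placed at the plateau target T and the device error is a normal distribution truncated to differences between 80 − T and 100 − T, with 80 retained pairs per plateau. At 82% no retained difference can be below −2.

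**Equal SD 2, no bias.** S = 2 and coverage is 95.0% at every level. With the window it is 96% at 97% and at 82%, and 93% at the two middle plateaus.

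**SDs 1/1.5/2/3, no bias.**
- No window: S = √[(1 + 2.25 + 4 + 9)/4] = √4.0625 = 2.02; limits ±3.95. At 82%: 2Φ(3.95/3) − 1 = 81%. Average over plateaus: 93.9%.
- Window: at 82% the retained mean is +1.28 and SD 2.19. M = 1.28/4 = 0.32, S = 1.82, limits −3.25 to +3.89. Coverage at 82% = [Φ(3.89/3) − Φ(−2/3)] / [1 − Φ(−2/3)] = (0.9025 − 0.2525)/0.7475 = 87%.

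**SDs 1.5/1.8/2.2/2.6, no bias.**
- No window: S = √[(2.25 + 3.24 + 4.84 + 6.76)/4] = √4.2725 = 2.07; limits ±4.05; 2Φ(4.05/2.6) − 1 = 88% at 82%.
- Window: M = 0.23, S = 1.91, limits −3.52 to +3.97; 92% at 82% and 91% at 87%.

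**Bias +3 at 82% only, SD 1.5.**
- No window: M = 3/4 = 0.75; S = √[2.25 + (3 × 0.75² + 2.25²)/4] = √3.9375 = 1.98; limits −3.14 to +4.64. At 82%: Φ((4.64 − 3)/1.5) = 86%; elsewhere 98%.
- Window: pooled bias 0.73, and again 86% at 82%.
- Slope on the targets: (−7.5 × 3)/125 = −0.18 per SpO2 point. The regression may well flag this, but as a trend. It would not locate the bias at 82% or move the limits.

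**Bias +1.5/−1.5/−1.5/+1.5, SD 1.5, no window.** M = 0. The slope on the targets is (7.5 × 1.5 − 2.5 × 1.5 + 2.5 × 1.5 − 7.5 × 1.5)/125 = 0; on the device averages, as the plan specifies, it is about 0.035 from plateau means. S = √(2.25 + 2.25) = 2.12 and limits are ±4.16. Coverage is 96.2% at every level, because the pooled SD absorbs the bias. The limits are misplaced rather than too narrow: level-specific limits would be −1.44 to 4.44 at 82% and −4.44 to 1.44 at 87%.

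**Percentage differences.** These rescale errors by at most 97/82 = 1.18 across the plateaus, so they cannot absorb a threefold change in SD.

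**Precision of a plateau limit.** 95% half-width = 1.96 × SD × √[1/n + 1.96²/(2(n − 1))]. With n = 80 independent pairs this is 0.38 SD. With n = 10 (readings within a subject fully correlated) it is 1.10 SD. An intraclass correlation of 0.5 gives effective n = 80/(1 + 7 × 0.5) ≈ 18.

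**The case against.** The strongest objection is that the loss is hypothetical. The documents give no SD for this device, and equal bias and SD cost essentially nothing. The only accuracy figure they contain, the reference device's ±2 digits (section 6), is flat over 70-100%, though it concerns the reference and not BrOxy M. The 95% is also not claimed level by level: the endpoint is one range, and average coverage stays near 94% even in the worst SD case above. The scatterplot is a second, informal check. All of this stands, and it makes the point conditional. It does not remove the case for using the four levels that the design creates.

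Some stronger readings are tempting, and the documents do not support them:
- **That limits of ±5.88 (1.96 × 3) are needed at 82%.** Section 17.2 keeps only readings of 80% or more, so differences below −2 cannot occur there when the reference reads 82%.
- **That the 100% ceiling makes equal spread implausible.** The 80% floor lies closer to its plateau (2 points) than the ceiling does (3 points). With a true SD of 2 everywhere, the retained SD is 1.76 at 97% and 1.59 at 82%.
- **That cancelling biases make the limits too narrow.** In the example above coverage stays at 96%; what is hidden is the bias.
- **That by-plateau reporting protects the pooled figures from interrupted subjects, whose retained readings come from the upper plateaus.** The pooled figures keep whatever imbalance they have. The minimum of 67 readings per third and up to two extra subjects address this in part.
- **That the conclusion should rest on the worst plateau.** Section 16.3.2 gives no numeric margin to judge it against, and the worst of four imprecise estimates favours noise.

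**Conclusion.** The point holds in conditional form. The plan reports one pooled bias and one pooled pair of limits, makes no analytic use of its four controlled levels, and has no formal check on spread or on non-linear bias.

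The size depends on assumed SDs and biases, with normal errors, the reference at target and equal numbers per plateau. It runs from no material loss, to coverage at 82% of about 87% or 92% under the two rising-SD patterns with the window applied (81% or 88% without it), to about 86% for a 3-point bias confined to 82%. In that last case the pooled bias shows only about 0.75.

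A reader might infer that the pooled limits will be wrong at 82%. The documents show only that they could be, and that the plan as written would give no level-specific estimate to settle it. This is an improvement worth making to the SpO2 analysis; it does not invalidate the study.

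**What to change.** In section 16.3.2, prespecify the mean difference, SD and limits of agreement for SpO2 at each of the four plateaus, from a method that allows for repeated readings within subject (for example plateau as a factor and subject as a random effect). Keep the pooled bias and limits as a summary. State that the 80% floor in section 17.2 truncates low readings at the 82% plateau, so that bias and limits there are read with that caveat: with an assumed true SD of 2 and no bias, 15.9% of readings would be dropped and the mean difference would shift by +0.58.

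This needs no extra subjects, readings or procedures, only a four-row table and a paragraph of analysis text. The downside is precision. Each plateau limit has a 95% half-width of about 0.38 SD if the 80 pairs are independent, and up to about 1.1 SD if readings within a subject are fully correlated. The by-plateau results should therefore be presented as estimates with intervals.

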7.2 ENDPOINTS

The **primary endpoint** of the study will be a comparison of the accuracy of SpO_2 and HR measurements obtained with BrOxy M with that obtained with the reference pulse oximeter in paired observations over a range between 80% and 100% SpO_2 .

For each subject, four different saturation plateaus will be set up (i.e. at 97%, 92%, 87% and 82% SpO_2), waiting 30" before starting to keep the SpO_2 level on each plateau for 2.5' in order to obtain 8 measurements in post-processing. These measurements will be at least 20" away from each other, for a total of 32 measurements for each subject, as summarized in Table 1.

The study will follow the procedures described in the standard ISO 80601-2-61:2017 "Medical electrical equipment - Part 2-61: particular requirements for basic safety and essential performance of pulse oximeter equipment".

As **secondary endpoints**, the following will be verified:

• whether any relation exists between the accuracy of BrOxy M for both SpO₂ and HR and subject skin pigmentations as measured with the Fitzpatrick scale.

Clinical Investigational Plan			
Protocol No.:	Version 1.0	Page 22 of 45	
01M2020-CH.LMD	Date: 22 December 2020	1.80 == 0. 10	

• that no adverse events related to the use of BrOxy M, besides a temporary slight skin irritation of the wrist, will occur.

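### The Bland-Altman limits pool 32 readings from each of 10 subjects with no subject term and no confidence interval, so for new wearers they are slightly too narrow and much less certain than 320 readings suggest

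*Combined protocol and SAP*

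**What the plan says.** Section 16.3.2 describes the Bland-Altman analysis as a way "to estimate an agreement interval, within which 95% of the differences of the second method, compared to the first one, fall". The plot puts the "difference of the two measurements for each sample on the vertical axis and the average of the two measurements on the horizontal axis", so each paired reading is one point. It adds a line at the mean difference and "lines to mark the upper and lower control limits of plus and minus 1.96*the standard deviation of the measurement differences".

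Section 16.2 fixes the data: "Analyses will regard 320 pair measurements", "that will be obtained from 10 healthy subjects". Section 10 gives the structure: "On each of the remaining 10 subjects, 32 paired measurements will be performed". Readings within a plateau are at least 20 seconds apart (Section 7.2).

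Nothing in Section 16 splits the differences into between-subject and within-subject parts or names a repeated-measures form of the limits. Section 16.3.2 does mention, as an option discussed in the literature, reference lines drawn from the standard error of the mean. It does not adopt that option. No numeric agreement margin is given: differences should be small, meaning not clinically important.

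**The concern.** Of the five routines in Section 16.3.2, only the limits of agreement show, in measurement units, how far a single BrOxy M reading may lie from the reference. The t test concerns the mean difference, the correlation and the concordance coefficient are unitless, and the regression looks for a trend.

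A study meant to confirm device performance needs to speak about wearers other than these 10. If the device reads a little high in one person and a little low in another, the 32 readings from a person share that offset. The plan itself allows for this when it asks whether accuracy is related to skin pigmentation, a trait of the subject. Two things then follow:

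- The plain SD of all readings slightly undercounts the between-subject part.
- The centre line and the between-subject spread rest on 10 people, however many readings each contributes.

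Lines drawn without an interval do not show this. Ten volunteers who happen to be alike would give narrow lines with nothing to warn the reader. Correcting the t test for repeated readings would leave these lines unchanged, so the point is separate from the test of mean bias.

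**Working it through.** **Inputs from the documents.** k = 10 subjects (12 if both additional subjects are enrolled, since the first subject is not analysed), m = 32 readings each (4 plateaus x 8), multiplier 1.96.

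**The plan's own figures.** 10 x 4 x 8 = 320, as stated. (Section 16.2 lists ambient air and then four target levels, 80 pairs each, which read literally gives 400; 320 holds with ambient air as one of the four levels, as in Table 1.) For a normal distribution with known mean and SD, +/-1.96 SD contains 95.0%.

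**Assumptions.** One-way random-effects model for the differences, normal, equal SD across plateaus, total SD = 1. The documents give no ICC, so a range from 0 to 0.7 is shown.

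**Step 1: size of the plain SD.** E[s²] = 1 - ICC x (m-1)/(km-1) = 1 - ICC x 31/319. At ICC 0.5 this is 1 - 0.0486 = 0.9514, and its square root is 0.9754, so the SD is 2.46% low.

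**Step 2: standard error (SE) of a limit if 320 readings are independent.** sqrt(1/320 + 1.96²/(2 x 319)) = sqrt(0.003125 + 0.006021) = 0.0956 SD.

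**Step 3: SE of a limit with repeated readings.**
- Var(mean) = (1 + 31 x ICC)/320.
- Var(s²) = [2 x 9 x (1 + 31 x ICC)² + 2 x 310 x (1 - ICC)²]/319².
- Var(limit) ≈ Var(mean) + 1.96² x Var(s²)/(4 E[s²]).

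At ICC 0.5: Var(mean) = 16.5/320 = 0.0516. Var(s²) = (4900.5 + 155)/101761 = 0.0497. Var(limit) ≈ 0.0516 + 3.8416 x 0.0497/3.806 = 0.1017, so SE ≈ 0.319. Simulation (40,000 studies per setting) gives 0.312.

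**Step 4: results for k = 10.** Coverage is the share of a new wearer's differences inside mean +/-1.96s, from simulation.

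| ICC | 0 | 0.1 | 0.3 | 0.5 | 0.7 |
|---|---|---|---|---|---|
| Effective n = 320/(1 + 31 x ICC) | 320 | 78 | 31 | 19 | 14 |
| SD too low by (%) | 0 | 0.5 | 1.5 | 2.5 | 3.5 |
| Mean coverage, new wearer (%) | 94.9 | 94.6 | 94.0 | 93.0 | 91.8 |
| 5th percentile of coverage (%) | 93.3 | 92.7 | 90.6 | 87.4 | 82.6 |
| SE of a limit (SD units) | 0.096 | 0.143 | 0.230 | 0.312 | 0.401 |
| Ratio to 0.0956 | 1.0 | 1.5 | 2.4 | 3.3 | 4.2 |

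Mean coverage at ICC 0.5 came out at 93.0 or 93.1 across runs. The last row uses the true SD. A study would compute the independent-readings SE from its own SD, which averages 0.9695 at ICC 0.5 and 0.9526 at ICC 0.7. The ratios then become 0.312/(0.0956 x 0.9695) = 3.4 and 0.401/(0.0956 x 0.9526) = 4.4.

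**With 12 subjects.** At ICC 0.1 / 0.3 / 0.5 / 0.7, mean coverage is 94.7 / 94.1 / 93.3 / 92.3% and the SE ratio is 1.5 / 2.4 / 3.3 / 4.2: nearly the same.

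**The study's own readings.** The share inside the study's own limits is 95.0 to 95.4% for ICC 0 to 0.7.

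**In SpO2 points.** With an assumed total SD of 2 points the true upper limit is 3.92. At ICC 0, 95% of studies would estimate it within about 3.92 +/- 1.96 x 0.096 x 2, that is 3.54 to 4.30. At ICC 0.3 / 0.5 / 0.7 the ranges are 2.97-4.79 / 2.61-5.11 / 2.26-5.40.

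**The remedy.** Limits built on the summed variance components remove the bias in the variance. Their mean coverage is still only 94.7 / 94.3 / 93.6 / 92.6% at ICC 0.1 / 0.3 / 0.5 / 0.7. A 95% MOVER interval (method of variance estimates recovery) for the limit, with 9 df between and 310 df within subjects, covered the true limit in 96-97% of studies.

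**The case against.** The case against is strong on several points.

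- **The narrowing is small.** On limits of +/-3.92 it is at most about 3.92 x 0.035 = 0.14 SpO2 points at ICC 0.7, beside a stated reference-device error of +/-2 digits (Section 6). This stands: narrowness is the minor part.
- **A reader might infer that the 95% statement is false.** The documents do not support that. The sentence speaks of estimating an interval, and for the study's own differences the limits do contain about 95% at every ICC tried. The shortfall concerns new wearers, a target the section does not name. Rewording the sentence would add little.
- **A reader might infer that uncertainty is ignored altogether.** Section 16.3.2 does mention confidence bounds. However, they are not adopted, and bounds from the standard error of the mean would not give the uncertainty of a limit.
- **A reader might charge the plan with a confidence interval that treats 320 readings as independent and so covers poorly.** The plan proposes no such interval for the limits, so that is not an error in it.
- **The ICC is unknown.** At 0 the limits are essentially nominal, and at 0.1 the loss of coverage is negligible. Even so, the SE of a limit at 0.1 is already 1.5 times the independent-readings value.
- **No pass/fail decision uses these lines.** With no numeric margin, a reader cannot conclude that the device would wrongly pass. The harm is a misleading impression of precision.

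What remains is that Section 16 has no subject term and no planned confidence interval for the limits.

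**Conclusion.** The point holds as a moderate, cheaply corrected weakness in the analysis of the primary endpoint. For any positive ICC, the planned limits are a little too narrow for new wearers: 0.5 to 3.5% in SD and 0.4 to 3.2 percentage points of coverage for ICC 0.1 to 0.7. The larger matter is precision. Over the same range the SE of a limit is about 1.5 to 4.4 times what 320 independent readings would give, and nothing planned would show it.

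This rests on assumed ICC values, normal differences and equal SD across plateaus. It also rests on reading one SD of all 320 differences into Sections 16.2 and 16.3.2, which do not use the word pooled. It does not show that the device agrees poorly or that the 95% description of the observed readings is wrong.

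**What to change.** In Section 16.3.2, for SpO2 and HR separately:

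1. Compute the SD for the limits as the square root of between-subject plus within-subject variance, from a one-way random-effects model with subject as the random factor.
2. Report each limit with a 95% CI that reflects the number of subjects, for example MOVER with k-1 df for the between-subject part (9 df for 10 subjects, 11 df for 12). This is the more important step.
3. Interpret agreement with these intervals shown. Do not add a rule that the outer bounds must pass: the plan has no numeric margin to judge them against.

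The cost is a paragraph of SAP text and a little more analysis work, with no extra subjects, visits or data. The downside is a less favourable stated agreement. For a true upper limit of 1.96 SD, the median 95% CI would run from 1.67 to 2.34 SD at ICC 0.1, 1.51 to 2.67 at 0.3, 1.37 to 2.96 at 0.5 and 1.22 to 3.23 at 0.7.
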